7.5.5 Study Lens Accountability

At the end of the study, worn study lenses will be returned to Visioncare Research (UK sites only) in cases labelled with the subject ID number and date of retrieval. Any remaining care solutions will be returned in the kit-boxes along with the completed Kit-box accountability form.

Accountability of kit-boxes, and lenses ordered, received, dispensed or otherwise disposed of will be conducted at the end of the trial.

7.5.6 Clinical Variables

A full assessment of ocular health will be performed at the Baseline Visit.

Table 3 summarizes the clinical measurements to be taken at each visit:

Table 3: Summary of clinical measurements

	Baseline	Dispensing	Follow-up (1-week, 1-month)	Exit
	Visit 1a	Visit 1b	Visits 2 & 3	
Sphero-cylindrical refraction	✓			✓
Best corrected (sphero-cyl) Monocular VA	✓			✓
Keratometry/ Topography	✓			
Wearing time	✓		✓	
Comfort (on insertion, during the day, prior to removal)	✓		✓	
Symptoms, problems & complaints	✓		✓	
Vision quality	✓		✓	
Subjective assessments	✓		✓	
Monocular HC DVA	✓	✓	✓	
Spherical over-refraction (SOR)	✓	✓	✓	
Monocular HC DVA with SOR	✓	✓	✓	
Binocular distance VA with CLs	✓	✓	✓	
Lens fit assessments	✓	✓	✓	
Lens surface (wetting, deposits)	✓	✓	✓	
Slit lamp findings	✓	✓ if required	✓	✓

7.6 Subject Discontinuation

Subjects will be discontinued from the study in the event of any of the following occurring:

- i. Unacceptable subjective discomfort (i.e. lens cannot be tolerated or worn)
- ii. Unacceptable slit lamp findings (i.e. clinically significant, Grade 3 or 4)
- iii. Unacceptable fit (i.e. lens too tight or too loose)
- iv. At the discretion of the investigator or the subject

In the event of discontinuation, the Study Exit eCRF must be completed and the study exit date recorded on the source document record. The investigator will indicate the primary reason for discontinuation by selecting one of the boxes provided on the Exit eCRF. Further details can be provided in the 'comments' section if necessary.

7.7 Unscheduled Visits

An unscheduled visit is defined as any follow-up that occurs outside the visit window of the scheduled visit. A visit is also classified as unscheduled if the subject is seen a second time within the scheduled visit window.

Investigators should try as far as possible to schedule follow-up visits within the window. If this is not possible, and the visit falls outside the window, a protocol deviation eCRF will be completed to document. The investigator might also judge that a follow-up visit is in the best interest of the subject and schedule two visits within the same window, e.g. follow-up of an adverse event. Unscheduled visits are also made available anytime at the subject's request.

Unscheduled visits will be recorded on the follow-up eCRF. All variables listed on the Unscheduled Visit must be completed unless the subject exhibits a condition that prohibits the completion of a full visit. If this is the case, a written explanation is required in the comments section (e.g. not using solution due to discomfort after use).

Presenting VA and slit lamp variables must always be completed and the reason for the visit and any actions taken must be indicated in the 'comments' section.

7.8 Study Completion

The study is completed when all subjects have finished the 1-month Visit or have been discontinued.

Worn study lenses will be retrieved from the subjects and, if requested, returned to Visioncare Research in appropriately labelled cases. Lenses to be returned will be stored in saline and refrigerated until shipping. Similarly, any remaining care solutions will be returned in the kit-boxes along with the completed Kit-box Accountability Form.

7.9 Site Training and Visits

A site evaluation will take place during a visit to the site (with the exception for sites that have a valid onsite Site Evaluation Visit conducted within the past two years). Additional clinical training will be conducted by online training which will include an audio PowerPoint presentation and multiple-choice questions.

Monitoring visits will be documented in the Monitoring Plan which is a separate document.

8 ADVERSE EVENTS

An adverse event (AE) is defined as an undesirable clinical occurrence whether it is considered to be device-related or not. All adverse events regardless of whether device-related or not, will be monitored and reported on throughout the study. Possible adverse events are summarized in Table 4 below.

The investigator will be required to judge whether or not an adverse event is device-related. Reoccurring device-related events from the same subject are usually tabulated as separate events. In the case where more than one diagnostic finding is associated with an adverse

event, the event will be counted as one event and categorized under the most significant of the findings.

The investigator will be required to report all adverse events to the study CRO and all care product related adverse events to the REC/IRB. The seriousness of an adverse event is categorized as serious, significant, or non-significant (see Table 4).

Table 4: Adverse Events by Severity

Serious	Significant	Non-significant
Result in, or have the potential to cause either permanent impairment of a body function or damage to a body structure and may necessitate medical or surgical intervention. They include but are not limited to:	Symptomatic and warrant discontinuation of contact lens wear (temporary or permanent). They include but are not limited to:	Usually asymptomatic and do not warrant discontinuation of contact lens wear (temporary or permanent). However, as a precautionary measure the Investigator may decide to take action. They include but are not limited to:
MK – Microbial keratitis Permanent reduction in best spectacle corrected visual acuity (≥ 2 lines) Central (4mm) corneal opacity Central corneal neovascularization Iritis Hypopyon Hyphema Penetration of Bowman's membrane Any untoward medical occurrence that results in death, is life-threatening, requires hospitalization or prolongation of existing hospitalization, results in persistent or significant disability/incapacity or is a congenital anomaly/birth defect	CLPU – Contact lens peripheral ulcer CLARE – Contact lens associated red eye Significant Infiltrative Event (S.I.E) SEAL – Superior epithelial arcuate lesion Corneal warpage SLK – Superior limbic keratoconjunctivitis Other significant \geq Grade 3 corneal findings (e.g. edema or abrasions) Any corneal event which necessitates lens wear discontinuation of > 2 weeks Non-CL related anterior segment events e.g. EKC – epidemic keratoconjunctivitis Temporary loss of ≥ 2 lines of Best Spectacle Corrected Visual Acuity New corneal scar without positive history	CLPC – Contact lens associated papillary conjunctivitis SPK – Superficial Punctate Keratitis Non-significant infiltrative event Blepharitis Meibomitis Contact dermatitis Localized allergic reactions, including solution-related ocular toxicity Conjunctivitis: Bacterial, Viral, Allergic Keratoconjunctivitis Any corneal event not explicitly defined as a serious or significant event which necessitates lens wear discontinuation < 2 weeks Other slit lamp findings requiring treatment

For additional information, questions or assistance in recording potential adverse events, contact Visioncare Research.

8.1 Adverse Event Categorization

The investigator will be required to rate the likelihood of an event being device-related (Possible, Probable, Highly Probable) or non-device-related (No) in their adverse event evaluation.

All device-related adverse events will be tabulated and reported in the final report.

8.2 Adverse Event Reporting

On finding an adverse event the investigator will complete an Adverse Event Form (AE eCRF) to document the condition.

The Investigator must notify Visioncare Research of any type of AE, so that they are able to provide advice and support to the Investigator on how to proceed.

The Investigator must do this by providing the information on the AE eCRF to Visioncare Research by eCRF, email, fax or telephone as soon as possible and no later than:

- 24 hours from discovery if event is Serious
- 2 working days from discovery if event is Significant or Non-Significant

Visioncare Research will advise the investigator to notify the REC/IRB no later than:

- Sterling IRB (US) reporting requirements, within 10 working days from the date of discovery.
- NRES REC (UK) reporting requirements, 15 working days from the date discovery.

Visioncare Research may notify the REC/IRB on behalf of the investigator.

To report to the REC/IRB send a covering letter with details as per the REC/IRB requirements. This usually includes the subject identifier and a brief description of how the AE was discovered, the subject's condition and any follow-up anticipated. The AE Form is also sent to the REC/IRB. These documents can be sent by fax or email depending on the individual REC/IRB facilities.

The investigator must also notify Visioncare Research in writing that the AE has been reported to the REC/IRB.

8.3 Device-Related Adverse Event Documentation

Investigators are required to document and follow-up all AEs.

All AEs are documented on an AE eCRF upon event discovery. One AE eCRF is used per eye.

Procedure:

The investigator has the responsibility to:

1. Complete as much information as possible on the AE eCRF upon event discovery. This includes:
 - A detailed description of the AE and a diagnosis, including a probable cause
 - Detailed drawings that detail size, location and depth or photographs (if necessary)
 - Likelihood of the AE being device-related and whether lens or care product-related.
2. If serious, collect any contact lenses worn, solutions, and the lens case used at the time.
3. Report the AE to the sponsor (via CRO, i.e. Visioncare Research) and the REC/IRB within the specified timelines (see Adverse Events section 8.2).
4. Follow study subject until resolution recording all information on an unscheduled visit eCRF, including VA, symptoms and slit lamp findings, resolution and permanent sequelae if any.

5. Complete all remaining information as required by the AE eCRF. If follow-up of the AE is required, the follow-up section can only be completed when all follow-up visits are done. Additional information that will be completed on the AE eCRF include:

- Outcome, ocular sequelae if any
- Whether the patient is discontinued from the study as a result of the AE

8.4 Adverse Event Follow-up

The Investigator will conduct follow-up examinations until the condition has either:

- Returned to pre-event status,
- Stabilized, or
- Been satisfactorily explained.

If the subject is referred for medical attention, they will be tracked by the investigator until the aforementioned conditions are met.

Follow-up data will be collected on Follow-up Visit eCRFs (marked as unscheduled visit) and on the AE eCRF.

If Corneal Staining is present of Grade 3 or more, another follow up visit should be scheduled within 24 hours.

The investigator should use his/her clinical judgement as to whether or not the subject reporting with an adverse event should continue in the study.

8.4.1 Sponsor Safety Responsibilities

The sponsor will ensure that all participating investigators are promptly informed of significant new safety information with respect to the device being studied as per regulatory bodies' requirements.

To comply with this, the sponsor is responsible for promptly advising (in writing, via Visioncare Research) all investigators conducting clinical studies using an investigational device, of any incidents of serious or unexpected adverse events/unanticipated adverse device effects reported for the devices/products involved in those studies.

9 DATA MANAGEMENT

9.1 Electronic Case Report Forms/Data Collection

The data for this study will be collected on electronic report forms (eCRFs) using an electronic data collection (EDC) system. Designated study site personnel will enter study data into the electronic CRFs (eCRFs) using the Medrio EDC system. Medrio is compliant with all relevant aspects of ICH/Good Clinical Practices and 21 CFR Part 11 (Electronic Records & Electronic Signatures) regulations.

9.2 Data Quality Assurance

When eCRFs are reviewed at Visioncare Research, they will be subjected to error checking and data queries will be raised electronically via the EDC system for resolution of omissions and discrepancies by the investigator.

Before the final closing of the database, the data will be checked and approved for analysis as per Visioncare Research SOPs. This includes checking for missing or erroneous data entries

9.3 Data Entry and Storage

All study data shall be entered into the study eCRFs. The statistical analyses will be completed by the CRO using SAS software (SAS Institute Inc., Version 9.4).

10 SAMPLE SIZE AND STATISTICAL METHODS

10.1 Sample Size Rationale

The sample size was selected to be in agreement with ISO 11980:2012. The sample size assumes a drop-out rate of <10% and was rounded up to allow for equal subject numbers and even enrolment at each site.

10.2 Statistical Analysis Plan

General considerations: All data summaries and statistical analyses will be performed using the SAS software Version 9.4 or higher (SAS Institute, Cary, NC). Throughout the analysis of data, the results for each subject/eye will be used when available for summarization and statistical analysis. Missing data will be excluded from the analysis. Unscheduled visits will be excluded from the statistical analysis.

Descriptive statistics will be reported by solution type at baseline, dispensing, and each follow-up visit according to ISO 11980:2012. Continuous variables will be summarized using sample size (N), mean, standard deviation (SD), minimum and maximum, and categorical data variables will be summarized using the sample size, frequency distribution (count and percentage of subjects or eyes in each category), mean, median and SD.

Analysis Population: Statistical Analysis for hypothesis testing will be performed on all evaluable subjects. All inference will be carried out with an overall type I error rate controlled at 0.05.

Analysis of comfort: Results will be analyzed using a linear mixed model including the experimental design factors: solution type, visit and their interaction will be included as fixed effect factors and site and subject as random effects.

Comparisons between the test and control solutions will be carried out using pairwise one-sided confidence intervals constructed for least-square mean differences (mean difference calculated as Test minus Control). Non-inferiority will be concluded if the lower confidence limit is greater than -1.0.

Analysis of visual acuity: Results will be analyzed using a linear mixed model including the experimental design factors: solution type, visit and their interaction will be included as fixed effect factors and site and subject as random effects.

Comparisons between the test and control solutions will be carried out using pairwise one-sided confidence intervals constructed for least-square mean differences (mean difference calculated as Test minus Control). Non-inferiority will be concluded if the upper confidence limit is less than +0.05 logMAR.

Analysis of wettability: Results will be analyzed using a linear mixed model including the experimental design factors: solution type, visit and their interaction will be included as fixed effect factors and site and subject as random effects.

Comparisons between the test and control solutions will be carried out using pairwise one-sided confidence intervals constructed for least-square mean differences (mean difference calculated as Test minus Control). Non-inferiority will be concluded if the lower confidence limit is greater than -0.5.

Analysis of deposits: Results will be analyzed using a linear mixed model including the experimental design factors: solution type, visit and their interaction will be included as fixed effect factors and site and subject as random effects.

Comparisons between the test and control solutions will be carried out using pairwise one-sided confidence intervals constructed for least-square mean differences (mean difference calculated as Test minus Control). Non-inferiority will be concluded if the upper confidence limit is less than +0.5.

Analysis of slit lamp findings: First the results will be averaged across each sector. Average results will be analyzed using a linear mixed model including the experimental design factors: solution type, visit and their interaction will be included as fixed effect factors and site and subject as random effects.

Comparisons between the test and control solutions will be carried out using pairwise one-sided confidence intervals constructed for least-square mean differences (mean difference calculated as Test minus Control). Non-inferiority will be concluded if the upper confidence limit is less than +0.5.

Additional analyses:

- Overall occurrence of slit lamp findings of Grade 2 or higher
- Overall occurrence of lens VA findings worse than 6/12 (20/40)
- Overall occurrence of clinically significant lens surface deposits (>Grade 1)
- Ocular adverse events.

Any deviations from the above analysis will be documented in the report.

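### Read literally, Section 10.2 leaves findings seen only at unscheduled visits out of the three overall-occurrence counts

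*Combined protocol and SAP*

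**What the plan says.** The exclusion stands in the general considerations that open Section 10.2: "Unscheduled visits will be excluded from the statistical analysis". No exception follows. The additional analyses at the end of that section include "Overall occurrence of slit lamp findings of Grade 2 or higher", together with matching counts of lens VA worse than 6/12 and of deposits above Grade 1. Ocular adverse events are a separate item in the same list.

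Section 7.7 gives the definition: "An unscheduled visit is defined as any follow-up that occurs outside the visit window of the scheduled visit". It adds: "A visit is also classified as unscheduled if the subject is seen a second time within the scheduled visit window". It also offers visits on request: "Unscheduled visits are also made available anytime". Presenting VA and slit lamp variables are mandatory at all of them. The other variables on the form may be omitted, with an explanation, when the subject's condition prevents a full visit.

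Section 7.2.1 allows a follow-up outside the window, in extreme situations, to be treated as scheduled after discussion with the CRA.

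**The concern.** A count described as overall would normally cover everything observed after dispensing. Here the plan requires the relevant data at unscheduled visits and then, on a literal reading, leaves them out. Visits prompted by a problem are more likely than routine ones to fall outside the windows, so the omitted visits are not a random sample.

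The slit lamp count matters because the models work on averaged grades. Section 10.2 averages slit lamp results across sectors before modelling, and Appendix 4 grades corneal staining in five sectors. An eye with Grade 2 in one sector and none elsewhere enters the model as 2/5 = 0.4. The Grade 2 or higher count is where such a finding would be visible.

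If losses are in proportion to arm size, both rates are too low but the difference between arms is preserved. If one arm has more problem visits, the comparison is distorted as well.

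**Working it through.** The plan gives no expected occurrence rate and no expected number of unscheduled visits, so there is no figure to reproduce. The check has five steps.

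**1. Scope of the rule.** The exclusion is in the general considerations for the whole of Section 10.2, and the counts are called analyses in that section. Unscheduled visits are also mentioned in Sections 5.3, 5.5, 7.7, 8.3 and 8.4. None of these returns their data to the counts.

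**2. Days on which a follow-up is unscheduled (Sections 7.2.1 and 7.7).** The windows are 7 ± 3 = days 4–10 and 30 ± 4 = days 26–34. Days 1–3 (3 days) and 11–25 (15 days) lie outside both, which is 18 of 34 days (53%). A second visit inside a window is also unscheduled.

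**3. Size per affected subject.** The denominators are the planned arms in Section 4.2, 133 test and 67 control. If k subjects in an arm of size n have the finding only at an unscheduled visit, the rate is too low by k/n. Every k is an assumption.

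| Lost, test v control | Test rate too low by | Control rate too low by | Difference hidden (test minus control) |
|---|---|---|---|
| 1 v 0 | 1/133 = 0.8 points | 0 | 0.8 |
| 0 v 1 | 0 | 1/67 = 1.5 points | −1.5 |
| 5 v 0 | 5/133 = 3.8 points | 0 | 3.8 |
| 4 v 2 | 4/133 = 3.0 points | 2/67 = 3.0 points | 0.0 |
| 0 v 3 | 0 | 3/67 = 4.5 points | −4.5 |

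Counted by eye with one eye affected, each loss is 1/266 = 0.4 points (test) or 1/134 = 0.7 points (control).

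**4. Would a scheduled visit see the finding anyway?** Assume visits on days 7 and 30, and onset equally likely on each of days 1–30. Days after 30 are left out because a completing subject exits at the 1-month visit. A finding lasting D days from onset day o is present at a scheduled visit if day 7 or day 30 lies in o to o + D − 1.

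- D = 3: onsets 5–7 and 28–30, 6/30 = 20%.
- D = 7: onsets 1–7 and 24–30, 14/30 = 47%.
- D = 14: onsets 1–7 and 17–30, 21/30 = 70%.

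Short-lived findings are therefore not reliably recovered, while longer ones mostly are.

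**5. Effect on the non-inferiority models.** As a stress case, suppose 7 test subjects and no controls stop at unscheduled visits and their stopping values are lost. Assumptions: comfort 2 at stopping against 8.0 otherwise, SD 1.5 to 2.0, one-sided 95% limits (z = 1.645), arms 133 and 67. With p = 7/133, the mean shift is p × (2 − 8.0) = −0.316. The test-arm variance is (1 − p) × SD² + p(1 − p) × 6², and the SE is unpooled.

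- Comfort: lower limit −0.73 (SD 1.5) or −0.84 (SD 2.0), against the margin of −1.0. The limit passes −1.0 only at 13 v 0 (−1.03, SD 1.5) or 11 v 0 (−1.04, SD 2.0).
- Slit lamp, with Grade 3 at stopping, 0.3 otherwise and SD 0.5 to 0.7: shift 7/133 × 2.7 = +0.142, upper limit 0.29 to 0.33, against +0.5.

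**The case against.** The strongest reply is textual. The same paragraph says that "results for each subject/eye will be used when available for summarization and statistical analysis", so it treats summarising and analysing as two activities, and it excludes unscheduled visits only from the second. An untested count labelled overall could be read as a summary across all visits. This reading is possible. But the plan lists the counts as analyses, and it ties descriptive statistics to baseline, dispensing and each follow-up visit. Two tenable readings that give different counts are a reason to clarify.

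The second reply is that adverse event reporting covers the gap. Most of this stands. Table 4 includes Grade 3 or higher corneal findings, SPK, solution-related toxicity, corneal events that interrupt lens wear, and slit lamp findings needing treatment. Grade 3 or 4 findings also lead to discontinuation with a recorded reason (Section 7.6). What remains is mainly untreated Grade 2 slit lamp findings that are not adverse events, reduced lens VA, and deposits, where these resolve before the next scheduled visit. Adverse event tables do not correct the occurrence counts themselves.

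Third, not every problem visit is unscheduled. Sections 7.2.1, 7.5.2 and 7.5.3 call for rescheduling over absent lenses or wear time only when the subject has no problem, so a first in-window problem visit can count as scheduled. Some unscheduled visits are only for lens loss or damage (Section 5.3). The Section 7.5 instruction to contact the investigator covers wear up to the 1-week visit. For days 11–25 the support is the general offer in Section 7.7.

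Exit data are not an assured substitute. Table 3 marks slit lamp at exit, but Section 7.5.4 lists only refraction and VA with that refraction.

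**Conclusion.** The point holds as a minor to moderate defect in wording. The exclusion has no stated exception, and applied literally it makes the three counts incomplete. The number of findings lost cannot be derived from the documents. The per-subject effect rests on the planned arm sizes. The recovery percentages rest on the assumed visit days, even onset and assumed durations.

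A reader might infer that safety findings at unscheduled visits disappear from the report, or that the non-inferiority conclusions are at risk. The documents support neither. Adverse events have their own reporting route. The counts carry no hypothesis or margin. Leaving unscheduled visits out of the visit-based models is defensible, because wear time before assessment is specified for the scheduled visits (1 to 3 hours at Visit 2, at least 2 hours at Visit 3). A changed non-inferiority conclusion needs an extreme and wholly one-sided loss, and subjects who stop after Visit 2 keep their 1-week data.

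The relation between Sections 7.2.1 and 7.7 is a separate, smaller matter. The former can be read as a limited exception to the latter, but it leaves a case-by-case decision that determines which data are analysed.

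**What to change.** In Section 10.2:

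- Limit the unscheduled-visit exclusion to the visit-based mixed models.
- State that the three occurrence counts include a finding at any post-dispensing visit, scheduled or unscheduled, counted once per subject or once per eye, and name the unit.
- For the VA count, use only VA measured with the study lens on. Exit VA is taken with spherocylindrical refraction, and presenting VA at an unscheduled visit may be without lenses.
- For the deposit count, use unscheduled visits only where deposits were recorded.

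Subjects with more visits have more chances to be counted. Report the number of unscheduled visits by arm and the scheduled-visit-only counts beside the all-visit counts.

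Separately, before unmasking, reconcile Sections 7.2.1 and 7.7 on when an out-of-window follow-up counts as scheduled.

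The cost is one or two sentences and a little programming. No new data are needed, because Section 7.7 already requires presenting VA and slit lamp. No further sensitivity analysis of the mixed models is needed for this point.

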7.2 Study Visits

7.2.1 Visit Schedule

There will be a maximum of four scheduled visits as follows:

Visit 1a: Baseline

Visit 1b: Lens issue (may be combined with Visit 1a)

Visit 2: 1 week follow-up (7 days \pm 3 days) – WT 1-3 hours

Visit 3: 1 month follow-up (30 days \pm 4 days)

A visit schedule form will be supplied to all sites which will list the visit windows and this can assist in arranging visits within the acceptable visit window.

The investigator should confirm with the subject that they are able to attend the follow-up visits within the visit window before enrolling them in the study. If, in extreme situations (sickness, unforeseen circumstances), the subject can only attend outside the visit window, the investigator should discuss with the CRA whether this visit can be considered a scheduled visit.

The 1-week, and 1-month follow-up visits may only take place when the subject attends wearing their lenses. If this is not the case and the subject is not experiencing any problems with their lenses or the study solutions, the appointment will be rescheduled, ideally within the visit window unless they are experiencing difficulty.

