7.5 Visit 1b: Lens Fitting and Dispensing

The subjects will undergo a trial fit with the randomly allocated study lens type. If the appropriate study lenses are not available, a dispensing visit will be scheduled for another day.

- i. Slit lamp – confirm continued eligibility if on a different day
- ii. Record the parameters of the lenses on the Dispensing eCRF (lens type / lot number, lens parameters, etc.).

The performance of the lenses should be assessed after 10-15 minutes settling time and the following variables will be assessed:

- iii. Subjective comfort (0-10)

- iv. Vision
 - Monocular HC DVA (with CL)
 - Spherical over-refraction (SOR)
 - Monocular HC DVA with SOR
 - Binocular distance VA with CLs (Snellen/logMAR to the nearest letter)
- v. Surface characteristics
 - Lens surface wetting (0-4) and reason if Grade 1 or less.
- vi. Lens fit
 - Centration (0-2)
 - Corneal coverage (Y/N)
 - Post-blink movement (0-4)
 - Tightness on push-up (0-4)
 - Overall fit acceptance (0-4) and reason if Grade 2 or less.

To be successfully dispensed, subjects must show >Grade 2 lens fit acceptance with the trial lens and must be correctable to 6/12 (20/40) (0.30 LogMAR) or better in each eye. Trial lenses must also show >Grade 1 wettability.

Modifications to optimize the lens power will be allowed.

If the lens fit is acceptable, the investigator will issue the care system (Kit-box containing solution, lens case and instructions) that the subject was randomized to, and complete the Kit-box Accountability Log. All kit-boxes must be accounted for, even if they are not dispensed.

- vii. The subject will be instructed to wear the lenses on a daily wear basis (at least 8 hours a day, 6 days per week) until the 1-week follow-up appointment, unless they experience a problem which warrants lens removal. In this case the subject should contact the investigator.
- viii. The investigator or a clinical assistant will review the Participant Information Guide with the subject, which describes the procedures for contact lens wear, lens care, handling, cleaning and disinfecting. Any subject, who does not follow instructions to a degree that, in the Sponsor or Investigator's opinion, jeopardizes the subject's wellbeing or the validity of the study, will be discontinued.
- ix. The investigator will complete the Source Document Record (Appendix 3).

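### Section 10.2 excludes unscheduled visits without exception, so the Grade 2+ slit lamp count can miss findings that Section 7.7 requires to be graded

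*Combined protocol and SAP*

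**What the plan says.** The rule is in the general considerations of Section 10.2: "Unscheduled visits will be excluded from the statistical analysis". Later in the same section, the additional analyses include an overall count of slit lamp findings at Grade 2 or above. Nothing there says which visits feed that count.

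Section 7.7 defines the excluded visits: "An unscheduled visit is defined as any follow-up that occurs outside the visit window of the scheduled visit". A second visit within the same window is also unscheduled, and subjects may request a visit at any time. Grading at these visits is compulsory: "Presenting VA and slit lamp variables must always be completed".

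Other provisions bear on the point:
- Section 7.5, item vii, tells subjects to wear the lenses daily up to the 1-week visit, "unless they experience a problem which warrants lens removal. In this case the subject should contact the investigator".
- Section 7.2.1 allows a late or early visit to be rescued in extreme situations: "the investigator should discuss with the CRA whether this visit can be considered a scheduled visit".
- Section 7.6 lists this ground for discontinuation: "Unacceptable slit lamp findings (i.e. clinically significant, Grade 3 or 4").
- Table 4 in Section 8 includes, among significant adverse events, other significant findings at or above "Grade 3 corneal findings (e.g. edema or abrasions").
- Table 3 ticks slit lamp findings at Exit, but the list of exit measurements in Section 7.5.4 has only refraction and acuity.

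**The concern.** Unscheduled visits are often prompted by a problem, so they are where a solution reaction may first be seen. The protocol collects the grade there and the analysis section then sets the visit aside. Corneal staining, limbal hyperemia and bulbar hyperemia are the three safety hypotheses in Section 2.1.2, and the Grade 2+ count is the planned summary that shows individual reactions and not arm means. If it omits reactions that were graded, it understates occurrence. Because 10.2 does not say which visits count, two analysts could also report different safety counts from the same database.

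**Working it through.** **1. When a finding falls outside the count.** The windows are 7 ± 3 days (days 4 to 10) and 30 ± 4 days (days 26 to 34). Days 1 to 3 and days 11 to 25 lie in neither window, so a follow-up then is unscheduled unless accepted as scheduled under 7.2.1. A Grade 2+ finding is missed only if it is first seen at an unscheduled visit and has gone, or the subject has left, before the next scheduled visit. A finding that persists to an in-window Visit 2 or 3, or that leads to exit at one, is counted.

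**2. The plan's own figures.** Section 4.2 gives 133 test and 67 control subjects. The synopsis aims for at least 180 completers and Section 10.1 assumes drop-out below 10%. 180/(1 − 0.10) = 200, and 200 × 2/3 = 133.3 and 200 × 1/3 = 66.7. Both reproduce. The plan states no SD and no expected rate of findings, so the number affected cannot be derived.

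**3. Effect on the count.** If k test subjects are omitted, the test rate is understated by k/133:
- k = 1: 0.8 percentage points
- k = 3: 2.3 points
- k = 6: 4.5 points

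With assumed test rates at scheduled visits of 2%, 5% and 10%, adding three omitted subjects gives 4.3%, 7.3% and 12.3%.

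The target allows about 20 leavers (200 − 180), roughly 13 test and 7 control. Treating every leaver as an omitted case is a ceiling for leavers only, since 7.6 also lists discomfort, fit and discretion. It gives 13/133 = 9.8% and 7/67 = 10.4%, so the between-solution difference moves by only −0.7 points. Completers whose finding resolved between visits would add an unknown number.

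**4. Effect on the models.** If k test subjects had grade g in place of 0, the test mean would shift by k × g/133, against a margin of 0.5:
- Grade 2: 0.015 (k = 1), 0.045 (k = 3), 0.090 (k = 6)
- Grade 3: 0.023 (k = 1), 0.068 (k = 3), 0.135 (k = 6)

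A shift of 0.5 needs 0.5 × 133/2 = 33.25, so 34 subjects at Grade 2, or 0.5 × 133/3 = 22.2, so 23 at Grade 3. Corneal staining is averaged over five sectors, so Grade 2 in one sector counts as 2/5 = 0.4 and the shift is smaller still.

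**5. Extreme one-sided case for hyperemia.** Assume that all 13 test leavers have grade g, no control leaver does, the other subjects in both arms have mean m and SD s, and each subject gives one value. The level is taken as one-sided 95%; 10.2 states only an overall 0.05. With p = 13/133 and d = g − m:

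upper limit = d·p + 1.645·√(v/133 + s²/67), where v = (1 − p)s² + p(1 − p)d²

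| g | m | s | Upper limit |
|---|---|---|---|
| 3 | 1 | 0 | 0.28 |
| 3 | 0 | 0 | 0.42 |
| 3 | 0.5 | 0.7 | 0.44 |
| 3 | 0.3 | 0.7 | 0.47 |
| 3 | 0.2 | 0.7 | 0.48 |
| 4 | 0 | 0 | 0.56 |

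The Grade 3 rows stay below 0.5 and the Grade 4 row passes it. Every test leaver reacting at Grade 4 with no control leaver reacting is not a plausible scenario.

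**The case against.** **The models need defined visits.** This stands in full. Visit 2 fixes wearing time at 1 to 3 hours because solution-induced staining is most evident then, and unscheduled visits have no such control.

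**The text may not exclude these visits from the count.** Section 10.2 elsewhere names summaries and statistical analyses separately, and the exclusion mentions only the latter. The word overall may mean any visit. Ocular adverse events sit in the same list, and nobody would drop those found at unscheduled visits, since Section 8.1 promises to tabulate device-related events. These points make the coverage ambiguous. They do not settle it, because nothing in 10.2 brings the visits back in.

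**Adverse events already capture most of this.** Table 4 covers Grade 3 or higher corneal findings and symptomatic events that stop wear. Its non-significant column adds superficial punctate keratitis, solution-related toxicity and slit lamp findings that need treatment. Section 8.4 then provides for follow-up: "The Investigator will conduct follow-up examinations until the condition has either" recovered, stabilised or been explained. This narrows the gap considerably. What remains is mainly Grade 2 staining or hyperemia that is untreated and not recorded as an event. The protocol's own threshold for clinical significance is Grade 3. An adverse-event table is still not a Grade 2+ rate by solution.

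**A stronger reading a reader might infer.** One could conclude that the exclusion hides Grade 3 and 4 discontinuations and so biases the non-inferiority tests. The documents do not support that. Such findings count if seen at an in-window visit, corneal ones are listed as adverse events, and step 4 shows that many affected subjects would be needed to move a mean by the margin.

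**Conclusion.** The point holds for one safety count only. As written, 10.2 most directly leaves out a Grade 2+ finding that is first graded at an unscheduled visit and gone, or followed by exit, before the next scheduled visit. The exclusion from the mixed models is sound.

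The number of subjects involved is not known and cannot be obtained from the documents. Each omitted test subject costs about 0.8 percentage points of the test rate. The comparison between solutions is distorted only if such findings differ by solution. The non-inferiority conclusions are unlikely to change. That judgement rests on the assumed means, SDs and grades in step 5 and is not a proof, since the Grade 4 case shows it is not a strict bound.

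The label is a cheap improvement of minor severity.

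**What to change.** Replace the exclusion sentence in 10.2 with: *Unscheduled visits do not enter the by-visit summaries or the mixed models. For the overall Grade 2+ slit lamp count, each subject is counted once, by solution, on the worst grade at any visit after dispensing, including unscheduled and early-exit visits.*

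The worst grade is preferable to the last because 8.4 follows events to recovery or stabilisation, so the last grade may be the recovered one.

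Add the slit lamp examination to the exit list in 7.5.4, to match Table 3. This matters only for exits before the 1-month visit.

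Two additions are optional: a table of worst post-dispensing grade by solution for early leavers, and a sensitivity analysis that puts each early leaver's worst grade in place of the missing 1-month value.

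The cost is one sentence and one line. Section 7.7 and Table 3 already require the examinations, and the sample size does not change. The downside is that unscheduled grades come at uncontrolled wearing times, so they belong in the safety count and not in the models. Subjects who never return remain ungraded.
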